**Study Design:**

This phase I clinical trial will define the recommended phase II dosing (RP2D) based on dose-limiting toxicities (DLTs) and the full toxicity profile of the combination of hCE1m6-NSCs and irinotecan using a standard "3 + 3" dose escalation schema in patients with recurrent highgrade gliomas who are undergoing a debulking craniotomy or stereotactic brain biopsy. Except for dose levels 1 and -1, where only 1 dose of NSCs will be given (these patients can continue to receive treatment with irinotecan every 2 weeks), NSCs will be administered intracranially on days 1 and 15, and irinotecan will be given intravenously 2 days later, on days 3 and 17 of a 28 day cycle. With subsequent cohorts of patients, the NSC dose will be increased as tolerated, but the dose of irinotecan will remain the same unless DLTs occur that necessitate lowering the dose of irinotecan. A Rickham reservoir/catheter system will be placed at the time of surgery for delivering repeat doses of NSCs intracranially. MRIs and PET/CT scans of the brain will be performed at least every two months (at the end of every even cycle of study treatment to evaluate response).

Three doses of NSCs will be assessed. The starting dose will be  $5 \times 10^7$  NSCs, which was well-tolerated in the first-in-human study of CD-expressing NSCs. Due to volume limitations for intracerebral administration, the highest dose of NSCs to be tested will be  $1.5 \times 10^8$  cells. Study participants will receive repeat cycles of study treatment (dose level 1 and -1 patients will only receive repeat doses of irinotecan) as long as they are tolerating the treatment well, and there is no evidence of progressive disease.

An important secondary objective of this study will be to determine the biologic activity of the hCE1m6-NSCs by measuring concentrations of SN-38 in brain interstitium using intracerebral microdialysis. The first 6 patients to enroll in the study and the last 8 patients in the expansion cohort will undergo microdialysis to collect data regarding intracerebral levels of irinotecan and SN-38 when patients are treated with the lowest and highest NSC doses. Please note, the same dose of NSCs ( $5 \times 10^7$ ) is given to patients on dose levels 1 and 2, so whether the first 6 patients are all treated on dose level 1 or the first 3 dose level 1 and the next 3 on dose level 2, they will all receive the same dose of NSCs.

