## **1 GOALS AND OBJECTIVES (SCIENTIFIC AIMS)**

### **Primary Objectives**

To define the recommended phase II doses (RP2D) of intracranially administered hCE1m6-NSCs in combination with intravenous irinotecan in patients with recurrent high grade glioma. The RP2D will be based on the maximum-tolerated dose (MTD), or if the MTD is not reached, the maximum feasible dose (MFD), and the full toxicity profile including toxicities associated with repeat doses of NSCs.

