The dose of irinotecan to be administered on this trial will be  $180\text{mg}/\text{m}^2$  every other week. This irinotecan dose and schedule is FDA approved for use in colorectal cancer patients as part of the combination chemotherapy regimen FOLFIRI, and is expected to be well tolerated in the glioma population. If this dose is found to be too toxic, the starting dose will be de-escalated first to  $150\text{mg}/\text{m}^2$  every other week, followed by a further dose de-escalation to  $125\text{ mg}/\text{m}^2$  every other week if necessary.

Study participants will receive repeat cycles of study treatment (dose level 1 and -1 patients will only receive repeat doses of irinotecan) as long as they are tolerating the treatment well, and there is no evidence of progressive disease.

An important secondary objective of this study will be to determine the biologic activity of the hCE1m6-NSCs by measuring concentrations of SN-38 in brain interstitium using intracerebral microdialysis. The first 6 patients to enroll in the study and the last 8 patients in the expansion cohort will undergo microdialysis to collect data regarding intracerebral levels of irinotecan and SN-38 when patients are treated with the lowest and highest NSC doses. Please note, the same dose of NSCs ( $5 \times 10^7$ ) is given to patients on dose levels 1 and 2, so whether the first 6 patients are all treated on dose level 1 or the first 3 dose level 1 and the next 3 on dose level 2, they will all receive the same dose of NSCs.

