### 5.1.2 Phase I Cohorts and Dose Escalation and De-escalation Criteria

Phase I Cohorts will be of 3 or 6 participants, as indicated by the dose-escalation criteria.

**Enrollment of the first 3 patients to a dose level will be staggered** by requiring that each of the first 3 patients be separately observed for 4 weeks (or until the DLT assessment period has ended) before the next patient can start treatment on that dose level.

Dose escalation will proceed through the identified doses without skipping any dose levels.

**To be counted for dose escalation**, a study patient must receive at least 80% of the assigned NSCs and 80% of the irinotecan for a particular dose level and be followed for 4 weeks OR have experienced a DLT as defined in Section 5.3.3.

All study patients enrolled are to be fully followed for toxicity; any study participant who is not evaluable for dose escalation will be replaced.

The NSC dose levels and irinotecan dose schedules are provided in Table 5.3.1. The first cohort will start at NSC dose level 1 and irinotecan schedule A.

The following dose escalation rules will be used, using the DLT definition as provided in Section 5.3.2:

- If 0/3 study participants experiences a DLT, the next cohort of 3 study patients will be treated at the next higher dose level.
- If 1/3 study participants experiences a DLT, the cohort will be expanded by another 3 study participants who will be treated at the same dose level for a total of 6 study participants.
- If 1/6 participants experiences a DLT, the next cohort of 3 study participants will be treated at the next higher dose level.
- If 2 or more participants of either a 3 participant or 6 participant cohort encounter a DLT, then the MTD has been exceeded. If applicable, three (more) participants will be enrolled at the next lower dose level.
- At least 6 patients will be treated at the MTD (or MFD, if the MTD is not reached).

If the 3+3 design rules indicate a need for de-escalation, the following will apply:

- If all DLTs in a dose level are attributed uniquely to irinotecan, then only the irinotecan schedule will de-escalate.
- If all DLTs in a dose level are attributed uniquely to NSCs, and are not attributed to 'NSCs with irinotecan', nor to irinotecan alone, then only the NSC dose level will de-escalate.

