- l. Inclusion/exclusion criteria. Source documentation providing investigator's confirmation that patient has met all eligibility criteria must be available prior to registration. In addition, source documentation by neurosurgeon that (a) a physical connection between the post-resection tumor cavity and cerebral ventricles is not anticipated, (b) a gross total resection is not anticipated, (c) the prospective participant is able to undergo neurosurgery, and (d) documentation that patient "needs a biopsy/craniotomy" is needed.
- m. Histology confirmation for to be performed by COH pathologist.
- n. Real-time histology confirmation to occur during surgery on fresh frozen section. See section 8.1 for pathology criteria. If confirmation of high grade glioma not obtained, all further study procedures will cease.
- o. Vital signs: Weight, heart rate, blood pressure, respiration rate, temp. Height required only at baseline. KPS not required at Day 2 and 3. See Appendix A for KPS scale.
- p. Participants no longer receiving NSCs (e.g. Dose Levels 1 and -1) may have their Day 15 assessments performed on Day 17, prior to irinotecan dosing.

- q. KPS and vital status only. Vital signs and Neuro-Physical exam are not required.
- r. Adverse events experienced by participants will be collected and recorded from signing of informed consent document up to 30 days of the last dose of study medication. The period for collection and recording of AEs is extended for participants with ongoing “reportable” adverse events that are related to study agent. Adverse event reporting begins for events that occur on Day 1 (day of neurosurgery).
- s. The only concomitant medication that needs to be documented in the case report form is whether the patient is taking dexamethasone (or another corticosteroid), and if so, what the dose is.
- t. For HLA testing, collect blood in 1 red top tube. Maintain at room temperature. Bring samples to COH Histocompatibility Laboratory.
- u. Participants who have already undergone UGT1A1 genotyping may use those results and do not the procedure repeated.

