### **Monitoring and Personnel Responsible for Monitoring**

The Protocol Management Team (PMT) consisting of the PI, collaborating investigators, CRA, protocol nurse, and statistician is responsible for monitoring the data and safety of this study, including implementation of the stopping rules for safety.

This study will use a phase I tracking log to monitor data and safety for dose escalation, recording doses administered and resultant adverse events. The tracking log will contain dose levels administered, DLT-defining adverse events, and documentation that the data from a dose level is complete before dose escalation. Those data and safety elements will be reported to the COH DSMC as applicable with the PMT report, which will be submitted quarterly from the anniversary date of activation, as noted in Table 3 below. Protocol specific data collection will include the following items: adverse events per dose level, patient outcomes, and protocol deviations.

A decision to escalate to the next dose level will be made by the PMT only after all patients on the current dose level have been observed for 4 weeks. Enrollment of the first 3 patients to a dose level will be staggered by requiring that each of the first 3 patients be separately observed for 4 weeks before the next patient can start treatment on that dose level.

Reporting of data and safety to the DSMC will occur on a quarterly basis using the PMT report until the last study patient has been observed for 4 weeks.

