## Reporting of Unanticipated Problems and Adverse Events

---

**Unanticipated Problems:** Unanticipated problems must be reported to the COH DSMC and IRB **within 5 calendar days** according to definitions and guidelines at <http://www.coh.org/hrpp/Pages/hrpp-policies.aspx>. Any unanticipated problem that occurs during the study conduct will be reported to the DSMC and IRB by submitting electronically in iRIS (<http://iris.coh.org>).

**Serious Adverse Events** - All SAEs occurring during this study, whether observed by the physician, nurse, or reported by the patient, will be reported according to definitions and guidelines at <http://www.coh.org/hrpp/Pages/hrpp-policies.aspx> and Table 1 below. Those SAEs that require expedited reporting will be submitted electronically in iRIS (<http://iris.coh.org/>).

**Adverse Events** - Adverse events will be monitored by the PMT. Adverse events that do not meet the criteria of serious OR are not unanticipated problems will be reported only in the continuation reports and PMT reports (see Table 11.4 below).

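### Section 11.2 ends quarterly PMT reports to the DSMC after the last patient's 4-week observation, while NSC dosing at levels 2-4 and adverse event collection may continue

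*Combined protocol and SAP*

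**What the plan says.** **End of routine reporting.** Section 11.2 (Monitoring and Personnel Responsible for Monitoring) places DSMC reporting on a "quarterly basis using the PMT report until the last study patient has been observed for 4 weeks". The sentence does not say when the 4 weeks begin. The preceding paragraph uses the same period for staggered entry, requiring that "each of the first 3 patients be separately observed for 4 weeks before the next patient can start treatment on that dose level". Section 5.3 (Phase I Cohorts and Dose Escalation and De-escalation Criteria) repeats the stagger and gives the end of the DLT assessment period as the alternative.

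**Reporting interval.** Table 11.2 asks for a report every 3 months for a Risk Level 4 study and shows no end date.

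**Treatment.** The Study Design part of the synopsis states that, except at levels 1 and -1, "NSCs will be administered intracranially on days 1 and 15, and irinotecan will be given intravenously 2 days later", in 28-day cycles. Section 2.9 adds: "Study participants will receive repeat cycles of study treatment". Section 5.1, item 12, fixes no number of cycles; treatment ends on progression, unacceptable toxicity, non-compliance or withdrawal of consent.

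**Objective and data.** The primary objective bases the recommended phase II dose on the MTD or MFD and on "the full toxicity profile including toxicities associated with repeat doses of NSCs". Table 10, footnote r, collects adverse events "up to 30 days of the last dose of study medication".

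**Route for other events.** Under Section 11.4, adverse events that are neither serious nor unanticipated problems "will be reported only in the continuation reports and PMT reports". The recipient of the continuation reports is not named there.

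**The concern.** The cut-off is tied to the period in which DLTs are counted, not to the period in which patients are exposed. DLTs are counted in cycle 1, including the safety assessments on Day 1 of cycle 2, so toxicity from later NSC doses must be learned from accumulating adverse event data. Section 2.4 (NSC Immunogenicity Data) says it is unknown whether immune responses to repeat exposure will limit these cells' usefulness, and that this trial will investigate it.

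A non-serious grade 2 allergic reaction to NSCs shows what could be missed. Table 7.2.4 provides for a hold and then resumption; Section 5.3 excludes allergic reactions from the DLT definition; the stopping rule in Section 5.6 counts only grade 4 allergic reactions. Unless such an event leads to hospitalization, is otherwise serious or is an unanticipated problem, the listed expedited timelines do not cover it. Several such events across late cycles would normally be noticed in a cumulative table with a count of doses given. After the cut-off, no such table is scheduled to go to the DSMC through PMT reports.

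**Working it through.** The plan gives no figure to reproduce. The check sets the time limits side by side and then counts doses.

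**Step 1: the limits.**

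| Item | Ends | Source |
|---|---|---|
| Quarterly PMT report to DSMC | last patient observed 4 weeks | Section 11.2 |
| 3-monthly interval, Risk Level 4 | no end stated | Table 11.2 |
| NSC dosing, levels 2-4 | no fixed cycle number | Section 5.1, item 12 |
| Adverse event collection | 30 days after last dose | Table 10, footnote r |
| Post-treatment contact | 30 days (+/- 2) after last study agent | Table 10, footnote h |

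Whenever the last patient continues past cycle 1, dosing and adverse event collection outlast the first limit.

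**Step 2: doses by day 28.** NSCs are scheduled on Days 1 and 15, so a patient at levels 2-4 has had 2 doses (1 repeat). Four expansion patients have their first NSC dose on Day 15 (Section 5.4) and have had 1 dose (no repeat). Under the alternating assignment in that section, the last enrollee could be one of them.

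**Step 3: doses after day 28.** Let n be the number of completed cycles, without delays. The documents do not give n; 2 to 6 is an assumption.

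- Day 1 start: total 2n, after the cut-off 2n - 2, share (2n - 2)/2n.
- Day 15 start: total 2n - 1, after the cut-off 2n - 2, share (2n - 2)/(2n - 1).

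| n | Day 1 start | Day 15 start |
|---|---|---|
| 2 | 2/4 = 50% | 2/3 = 67% |
| 3 | 4/6 = 67% | 4/5 = 80% |
| 6 | 10/12 = 83% | 10/11 = 91% |

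These are shares of one patient's doses. Any other patient still on treatment at that date is affected too.

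**Step 4: other milestones.** The last patient's first scheduled response imaging is at the end of cycle 2, about day 56 (2 x 28), and the 3-month RCR test is later still. Both fall after the cut-off. A 4-week window also need not contain a quarterly due date, so on a literal reading the final report could predate this patient's treatment.

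**The case against.** The strongest reply is that DSMC oversight does not stop, and that is right. Table 11.4 sends serious grade 3-4 events to the DSMC within 5 or 10 days, even when judged unrelated, and also covers grade 1-2 events that lead to hospitalization and deaths on treatment. Unanticipated problems go to the DSMC within 5 days, IND safety reports are copied to it, and deviations are reported within 5 days (Section 14.2). A reader might infer that the committee is left blind; the documents do not support that. These are reports of single events, however, without a cumulative table or denominator. The promise in Section 11.2 to report concerns as they arise is tied to long-term follow-up, which Section 5.7 places after active treatment, so it does not clearly cover patients still being dosed.

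Other stronger readings also fail:

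- Non-serious events do not travel only through PMT reports. Section 11.4 also names continuation reports, so one cannot say that all cumulative reporting disappears.
- The cut-off does not hand the stopping rules to the PMT. Section 11.2 gives the PMT that task throughout the trial.
- No data are lost to the dose recommendation. Adverse events are still collected and are tabulated by dose and course (Section 15.3).
- Much repeat dosing will come under quarterly review, because levels 2-4 accrue in sequence with staggered entry. If level 4 is the MTD/MFD, its 6 patients count toward the expansion cohort of 8, so few late enrollees may remain.

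Finally, Table 11.2 has no end date, and the institutional monitoring plan cited in Section 11.1 is not among the documents; it may require reporting to continue. This makes the conflict one to reconcile, but does not remove the sentence that ends the reports.

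**Conclusion.** The point holds in a limited form. As written, Section 11.2 lets scheduled PMT reports to the DSMC end while patients at levels 2-4 may still be receiving NSCs and adverse events are still being collected. The loss is periodic cumulative DSMC review through that channel, chiefly of non-serious repeat-dose toxicity.

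For the last patient, the share of NSC doses after the cut-off is 50% to 83%, or 67% to 91% with a Day 15 start. This rests on two assumptions: that the 4 weeks run from that patient's treatment start, which is the natural reading but is not stated, and that treatment lasts 2 to 6 cycles without delay. It should not be read as a share of the trial's repeat-dose exposure. Patients at levels 1 and -1 receive a single NSC dose and continue irinotecan only, so the dose count does not apply to them.

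The sentence should be corrected: it conflicts with the exposure and data-collection periods and with the emphasis on repeat-dose toxicity in the primary objective.

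**What to change.** In Section 11.2, replace the end point so that quarterly PMT reports to the DSMC continue until the last patient remaining on study treatment has completed the 30-day post-treatment assessment (Table 10, footnote h). State that each report gives cumulative adverse events by cycle and by number of NSC doses received. Reconcile the sentence with Table 11.2 so that interval and end date agree.

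The cost is a short text change and a few more quarterly reports from data already collected. It adds no patients, visits or procedures, and changes no dose or clinical rule.

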**Table 11.2 City of Hope PMT Reporting Timelines for the DSMC**

Risk Level	Phase	Standard Reporting Requirement
RL 1, RL2, and Compassionate Use Studies	No reports required	
3	I	Every 3 months from activation date, as indicated in MIDAS
3	Pilot, Feasibility, II-IV	Every 6 months from activation date, as indicated in MIDAS
4	Pilot, Feasibility, I-IV	Every 3 months from activation date, as indicated in MIDAS

Data and safety will also be reported to the FDA. All IND safety reports that are submitted to the FDA regarding this protocol will also be submitted to the DSMC for review. As required by the FDA, study patients will be followed long term (up to 15 years or until death; see section 5.16), and the PMT will continue to report data and safety concern to the FDA, City of Hope DSMC, and IRB as they arise during this follow-up period.

## Definitions

---

**Adverse event (AE)** - An adverse event is any untoward medical experience or change of an existing condition that occurs during or after treatment, whether or not it is considered to be related to the protocol intervention.

**Unexpected Adverse Event [21 CFR 312.32 (a)]** - An adverse event is unexpected if it is not listed in the investigator's brochure and/or package insert; is not listed at the specificity or severity that has been observed; is not consistent with the risk information described in the protocol and/or consent; is not an expected natural progression of any underlying disease, disorder, condition, or predisposed risk factor of the research participant experiencing the adverse event.

**Expected Adverse Event** - Any event that does not meet the criteria for an unexpected event OR is an expected natural progression of any underlying disease, disorder, condition, or predisposed risk factor of the research participant experiencing the adverse event

**Serious Adverse Event (SAE)** [21 CFR 312.32] is defined as *any expected or unexpected adverse event* that results in any of the following outcomes:

- Death
- Is life-threatening experiences (places the subject at immediate risk of death from the event as it occurred);
- Unplanned hospitalization equal or greater than 24 hours)) or prolongation of existing hospitalization;
- A persistent or significant disability/incapacity;
- A congenital anomaly/birth defect
- Secondary Malignancy, or
- Any other adverse event that, based upon appropriate medical judgment, may jeopardize the subject's health and may require medical or surgical intervention to prevent one of the outcomes listed above (examples of such events include allergic bronchospasm requiring intensive treatment in the emergency room or at home, blood dyscrasias of convulsions that do not result in inpatient hospitalization, or the development of drug dependency or drug abuse).

**Unanticipated problem (UP)** – Any incident, experience or outcome that meets all three of the following criteria:

1. Unexpected (in term nature, severity, or frequency) given the following: a) the research procedures described in the protocol-related documents such as the IRB approved research protocol, informed consent document or Investigator Brochure (IB); and b) the characteristics of the subject population being studied; **AND**
2. Related or possibly related to participation in the research (possibly related means there is a reasonable possibility that the incident, experience, or outcomes may have been caused by the agents, devices or procedures involved in the research); **AND**
3. Suggests that the research places subjects or others at greater risk of harm (including physical, psychological, economic, or social harm) than previously known or recognized.

## Reporting of Unanticipated Problems and Adverse Events

---

**Unanticipated Problems:** Unanticipated problems must be reported to the COH DSMC and IRB **within 5 calendar days** according to definitions and guidelines at <http://www.coh.org/hrpp/Pages/hrpp-policies.aspx>. Any unanticipated problem that occurs during the study conduct will be reported to the DSMC and IRB by submitting electronically in iRIS (<http://iris.coh.org>).

**Serious Adverse Events** - All SAEs occurring during this study, whether observed by the physician, nurse, or reported by the patient, will be reported according to definitions and guidelines at <http://www.coh.org/hrpp/Pages/hrpp-policies.aspx> and Table 1 below. Those SAEs that require expedited reporting will be submitted electronically in iRIS (<http://iris.coh.org/>).

**Adverse Events** - Adverse events will be monitored by the PMT. Adverse events that do not meet the criteria of serious OR are not unanticipated problems will be reported only in the continuation reports and PMT reports (see Table 11.4 below).

